#### Table 7-1Outcomes/endpoints collected in the survey

| Study objective domains assessed   | Corresponding variable (original data collected;
all are categorical variables)  | Operational
definition/derivation
"Calculated as the
percentage of HCPs
who" |
|--|---|--|
| HCPs' knowledge of the risk for hyperglycemia and                                      | Knowledge that hyperglycemia is a risk associated with treatment with Piqray (key question)   | "Checked" question 4A  |
| risk factors for
hyperglycemia  | Knowledge that pneumonitis is a risk associated with treatment with Piqray  | "Checked" question 4B  |
|  | Knowledge that severe cutaneous reactions are a risk associated with treatment with Piqray  | "Checked" question 4C  |
|  | Knowledge that suicidal ideation is not a risk associated with treatment with Piqray  | "Not checked" question
4D   |
|  | Knowledge that onychomycosis is not a risk associated with treatment with Piqray  | "Not checked" question 4E  |
|  | Knowledge that being diabetic/pre-diabetic, having a fasting blood glucose >13.9 mmol/L( 250 mg/dL), and being 75 years of age or older are additional risk factors for developing hyperglycemia while taking Piqray (key question) | "Checked" only "body
mass index <30
kg/m  "for question 6              |
| HCPs' knowledge of the
signs and symptoms of  | Knowledge that excessive thirst is a sign/symptom of hyperglycemia (key question)   | "Checked" question 5A  |
| hyperglycemia  | Knowledge that increased frequency or amount of urination is a sign/symptom of hyperglycemia (key question)   | "Checked" question 5B  |
|  | Knowledge that increased appetite with weight loss is a sign/symptom of hyperglycemia (key question)  | "Checked" question 5C  |
|  | Knowledge that inability to swallow is not a sign/symptom of hyperglycemia  | "Not checked" question 5D  |
|  | Knowledge that yellowing of the skin is not a
sign/symptom of hyperglycemia  | "Not checked" question 5E  |
|  | Knowledge that difficulty breathing is a sign/symptom of hyperglycemia (key question)   | "Checked" question 5F  |
|  | Knowledge that nausea and/or vomiting is a sign/symptom of hyperglycemia (key question)   | "Checked" question 5G  |
|  | Knowledge that headache is a sign/symptom of hyperglycemia (key question)   | "Checked" question 5H  |
| HCPs' knowledge of
recommendations for
monitoring for
hyperglycemia prior to, | Knowledge that for patients at higher risk for
developing hyperglycemia, an HCP/endocrinologist
experienced in the treatment of hyperglycemia
should be consulted  | Checked "false" to question 7  |
| and during, treatment with
Piqray   | Knowledge that a fasting glucose and HbA1c should
be obtained before a patient starts treatment with
Piqray (key question)  | "Checked" question 8A  |
|  | Knowledge that the patient's level of blood glucose
should be optimized, as applicable, before a patient
starts treatment with Piqray (key question)  | "Checked" question 8B  |

| Study objective domains assessed   | Corresponding variable (original data collected;
all are categorical variables)  | Operational
definition/derivation
"Calculated as the
percentage of HCPs
who"   |
|--|---|--|
|  | Knowledge that the patient should be counselled
about the risk of hyperglycemia before a patient
starts treatment with Piqray (key question)  | "Checked" question 8C  |
|  | Knowledge that the dose of their current
antihyperglycemia medication, if applicable, does
not need to be increased before a patient starts
treatment with Piqray  | "Not checked" question
8D   |
|  | Knowledge that the Piqray Prescriber's/HCP
Guide for Hyperglycemia and SmPC does not
require a diabetologist to be consulted for patients
who are not diabetic before a patient starts
treatment with Piqray  | "Not checked" question
8E   |
|  | Knowledge that "the monitoring schedule of fasting
glucose levels for patients receiving Piqray is the
same for all patients with, and without, risk factors
for hyperglycemia" is not correct   | Checked "false" to question 9  |
|  | Knowledge of when a FPG test should be performed after starting treatment with Piqray (key question)  | Checked "at weeks 1, 2,
4, 6, and 8, after
treatment start, then
monthly thereafter" to
question 10  |
|  | Knowledge of the frequency for HbA1c testing to be performed for all patients treated with Piqray   | Checked "4 weeks after
treatment start, then
every 3 months
thereafter" to question 11  |
|  | Knowledge of what frequency should fasting glucose
be monitored when hyperglycemia occurs and
patients are treated with antihyperglycemic
medications (key question)   | Checked "weekly for at
least 8 weeks, followed
by once every 2 weeks,
and consider
consultation with a
healthcare professional
with expertise in the
treatment of
hyperglycemia" to
question 15 |
| HCPs' knowledge of
recommendations for
managing hyperglycemia
during treatment with
Piqray | Knowledge that for fasting glucose values that are
≤250 mg/dL (≤13.9 mmol/L), no Piqray dose
adjustment is required, and it is recommended to
manage by initiating or intensifying oral
antihyperglycemic treatment (key question)                  | Checked "true" to
question 12   |
|  | Knowledge of which fasting glucose values require
Piqray dosing to be interrupted (key question)   | Checked "any fasting
glucose value >250
mg/dL (>13.9 mmol/L) to
question 13   |
|  | Knowledge that "if Piqray dosing is interrupted due
to elevations in fasting glucose >250 mg/dL (>13.9
mmol/L), and fasting glucose decreases to <160
mg/dL (<8.9 mmol/L) within 3-5 days under
appropriate antihyperglycemia treatment, Piqray can | Checked "false" to
question 14  |

| Study objective domains assessed   | Corresponding variable (original data collected;
all are categorical variables)  | Operational
definition/derivation
"Calculated as the
percentage of HCPs
who" |  |
|--|---|--|--|
|  | be resumed at the starting dose level of 300 mg/day" is not accurate (key question)   |  |  |
| Assess whether HCPs received and read the  | Received the Guide for HCPs   | Checked "Yes" to
question 1   |  |
| Piqray Prescriber's/HCP
Guide for Hyperglycemia   | Read the Guide for HCPs   | Checked "Yes, all of it" +
"Yes, some of it" to
question 2                         |  |
| Primary source of the
indication, precautions for
use, and potential risks for
Piqray | Response choices: Piqray SmPC, Piqray Guide for
HCPs , NCA website, Professional society or
congress, Piqray product website, EMA website,
Clinical practice guidelines, Novartis representative,
Other | Checked each of the response choices to question 3                                       |  |

Note: Please see Appendix 13.1 for a full list of survey questions

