#### 7.3.1 **Outcomes/endpoint variables**

Primary endpoint:

- Levels of knowledge of the risk for hyperglycemia, and risk factors for hyperglycemia, (survey question 4A, 6),
- Levels of knowledge of signs and symptoms of hyperglycemia (survey questions 5A-C), •
- Levels of knowledge of recommendations for monitoring for hyperglycemia prior to, and during, treatment with Pigray (survey questions 8A-C, 10, 15) and
- Levels of knowledge of recommendations for managing hyperglycemia during treatment ٠ with Piqray (survey questions 12-14).

The primary endpoint is a composite endpoint that combines correct responses given by HCPs to questions included in the composite. Specifically, the primary endpoint is a weighted composite knowledge score aggregated across the following survey questions: 4A, 5A-C, 6, 8A-C. 10, and 12-15. It is calculated as the number of all correctly answered questions divided by the number of all answered questions (i.e. questions that were answered either correct and not correct – unanswered questions are excluded).

Success criteria on the primary endpoint is defined as a weighted composite knowledge level of at least 70% across these key questions.

Secondary endpoint questions:

- Levels of reported receipt and reading of the Pigray Prescriber's/HCP Guide for • hyperglycemia, assessed as the percentages of HCPs who report receipt and reading of the same (survey questions 1, 2)
- HCPs' knowledge levels for each survey question regarding knowledge of, and • management of, hyperglycemia, assessed as the percentages of HCPs with correct responses to each question (individual responses to survey questions 4-15)
- The distribution of responses regarding the primary source from which HCPs learned • about the messages included in the Piqray Prescriber's/HCP Guide for Hyperglycemia, assessed as the percentages of HCPs who report using each of the possible sources as the primary source they used (survey question 3).

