## 7.7.1 Analysis populations

The primary analysis set will include all HCPs who have completed at least one of the endpoint questions in the survey. Denominators used to calculate descriptive statistics for each survey question will reflect the number of respondents who completed that particular question including responses of "I don't know/am not sure".

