## [ON-LINE SURVEY - PROGRAMMER: RANDOMIZE THE ORDER OF THE FIRST 8 RESPONSE OPTIONS]

| Novarti   | is                              | Confidential  |                               |
|---|---------------------------------|---|-------------------------------|
| Non-In  | terventional Study Protocol v00 |   | BYL719/alpelisib/CBYL719C2005 |
| 
 
Listed below are several risks.
Piqray?
 
 |                                 | ich of these risks are asso                           | ciated with treatment with    |
|   |                                 | Check the box if
associated with
treatment with |                               |

|   |                              | Piqray |
|---|------------------------------|--------|
| А | Hyperglycemia [KEY QUESTION] | 1      |
| В | Pneumonitis                  | 1      |
| С | Severe cutaneous reactions   | 1      |
| D | Suicidal ideation            |        |
| Е | Onychomycosis                |        |
| F | I don't know/am not sure     |        |

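### Table 7-1 credits respondents who tick only the don't-know row with knowledge on six non-key distractor items, so the secondary results for those items are overstated

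*Protocol*

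**What the plan says.** Table 7-1 in Protocol section 7.3.1 defines each knowledge level as the percentage of HCPs who meet a stated condition. For six items that condition is an empty box:

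- Question 4: the row on item 4D is labelled "Knowledge that suicidal ideation is not a risk associated with treatment with Piqray" and is scored on the box being empty. Item 4E reads "Not checked' question 4E".
- Question 5: "Not checked' question 5D" and "Not checked' question 5E".
- Question 8: "Not checked' question 8D", and the same rule for 8E.

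In Appendix 13.1, questions 4, 5 and 8 are tick-box grids. Each has a further row, "I don't know/am not sure", as 4F, 5I and 8F.

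On denominators, section 7.7.1 says: "Denominators used to calculate descriptive statistics for each survey question will reflect the number of respondents who completed that particular question including responses of" the don't-know option.

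The six items feed the secondary endpoint on knowledge per question, which section 7.3.1 describes as "assessed as the percentages of HCPs with correct responses to each question (individual responses to survey questions 4-15").

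The protocol nowhere says that ticking 4F, 5I or 8F stops an empty distractor box from counting as correct. The programming notes beside the grids deal with the order of the rows. They do not make the don't-know row exclusive.

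**The concern.** In a tick-all-that-apply grid, an empty box can mean that the respondent considered the statement and rejected it, or that the respondent did not know. The questionnaire offers a row that separates the two, but the scoring rule ignores it. A respondent who ticks only 4F is scored as not knowing 4A to 4C, where a tick is required, and as knowing 4D and 4E, where an empty box is required. One admission of uncertainty is thus read in opposite ways within the same question.

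The single-choice items do not have this problem. For questions 6, 7 and 9 to 15, Table 7-1 requires a particular answer, so don't know can never be correct.

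At stake is how six of the per-question results are read. Their reported knowledge level rises as admitted ignorance rises. Two of them (8D and 8E) concern actions before treatment starts, and two (5D and 5E) concern the signs of hyperglycemia.

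**Working it through.** The protocol states no figure for this quantity, so there is none to reproduce. The check is to apply the scoring rule literally and then work out the size.

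**Step 1: score a respondent who ticks only the don't-know row.**

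| Question | Row ticked | Items that need a tick | Items that need an empty box |
|---|---|---|---|
| 4 | 4F | 4A, 4B, 4C: not correct | 4D, 4E: correct |
| 5 | 5I | 5A, 5B, 5C, 5F, 5G, 5H: not correct | 5D, 5E: correct |
| 8 | 8F | 8A, 8B, 8C: not correct | 8D, 8E: correct |

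This respondent has answered the question for the purposes of section 7.7.1 and so stays in the denominator. Someone who does this in all three grids scores 6 of 6 on the distractors.

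**Step 2: size of the effect.** Let d be the share of respondents to a question who tick only the don't-know row, and k the share of the others who leave the distractor empty.

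- Score under Table 7-1: d + (1 − d)k
- Score with don't know counted as not correct: (1 − d)k
- Difference: d, whatever the value of k

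**Step 3: numbers.** The sample size n = 50 is the upper end of the 30 to 50 completed surveys in section 7.5. The values of d and k are assumptions; the protocol gives neither.

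| d | k | Don't know only | Others leaving box empty | Table 7-1 score | Don't know as not correct | Difference |
|---|---|---|---|---|---|---|
| 10% | 60% | 5 | 0.60 × 45 = 27 | 32/50 = 64% | 27/50 = 54% | 10 points |
| 20% | 60% | 10 | 0.60 × 40 = 24 | 34/50 = 68% | 24/50 = 48% | 20 points |
| 20% | 80% | 10 | 0.80 × 40 = 32 | 42/50 = 84% | 32/50 = 64% | 20 points |
| 30% | 60% | 15 | 0.60 × 35 = 21 | 36/50 = 72% | 21/50 = 42% | 30 points |

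The second and third rows share the same d and show that k does not matter. Without assuming any d, each such respondent adds 100/50 = 2 points at n = 50, or 100/30 = 3.3 points at n = 30. At the extremes, d = 0 gives no overstatement, and d = 100% would show every one of the six items at 100% knowledge.

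**Step 4: reach.** Section 7.3.1 builds the primary composite from 4A, 5A-C, 6, 8A-C, 10 and 12-15. None of the six items is in that list, and none is marked as a key question in Table 7-1. The effect on the composite is zero.

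**The case against.** The strongest case on the other side is that little hangs on this. The six items are non-key foils, reported descriptively with no success threshold of their own, and 4D and 4E do not concern hyperglycemia. Respondents must have prescribed Piqray within the previous six months, so few may tick only don't know. A statistical analysis plan is promised in section 7.7 and could settle how the don't-know row interacts with the others. All of this limits the weight of the point. It does not remove it: Table 7-1 already fixes the derivation, so an analysis plan would have to override it, not fill a gap.

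Four stronger readings are tempting, and the documents do not support them.

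- **The primary result is inflated.** It is not, because none of the six items enters the composite and nothing in the protocol proposes adding them.
- **An HCP who ticks nothing in a grid is also credited.** Section 7.7.1 limits each denominator to respondents who completed the question, and section 7.7.2 provides a missing category. Each of the three grids has at least three correct rows plus a don't-know row, so a wholly empty grid can reasonably be recognised as unanswered. It is still worth stating this in the rule.
- **The bias equals the share who tick don't know at all.** As the grids stand, someone can tick 4A to 4C together with 4F, meaning doubt about the remaining rows, or tick 4D with 4F and already be scored wrong. The formula above holds only for those who tick the don't-know row and nothing else.
- **Don't know should be scored wrong on every row of the grid.** That would also rescore 4A, 5A-C and 8A-C, which are primary items, for anyone who ticks both. The problem found here does not call for that.

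**Conclusion.** The rule as written gives a wrong result for six secondary items: a respondent who answers only don't know is counted as knowledgeable on them. The overstatement equals the share of such respondents on each grid. That share is unknown; it would be 10, 20 or 30 points for assumed shares of 10%, 20% or 30%, and nothing if nobody answers in this way. The direction is certain, since the error can only raise these percentages. The conclusion assumes that Table 7-1 is applied literally and that no rule outside the protocol overrides it. The primary composite and the 70% criterion stand as they are. This is a modest but clear defect in a stated derivation, worth correcting before the survey is programmed.

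**What to change.** In Table 7-1, define 4D, 4E, 5D, 5E, 8D and 8E as correct only if all three conditions hold: the box is not ticked, at least one substantive option in the same grid is ticked, and the don't-know row is not ticked. Count don't know as not correct on these six items and keep it in the denominator, in line with section 7.7.1. State that a wholly blank grid is unanswered and reported as missing. In Appendix 13.1, program 4F, 5I and 8F as mutually exclusive with the other rows of their grids.

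The cost is six derivation lines, one sentence on blank grids and one programming rule per grid. The reported percentages for these six items will become somewhat less favourable. The exclusivity rule has one side effect: a respondent who would have ticked a key row and don't know together must choose between them. The scoring of the key items in Table 7-1 does not change.

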## 6 Research question and objectives

The objective of this survey, amongst oncologists/HCPs prescribing Piqray in selected countries in the EU/EEA, is to confirm that they received the educational material and to assess their knowledge, understanding and management of hyperglycemia in patients treated with Piqray.

Assessing, firstly, the dissemination of the educational material, and upon receipt of the material assess prescribing physicians' knowledge, understanding and behavior relating to the management of hyperglycemia as detailed in the educational material and SmPC provided. The educational material provides additional guidance to the SmPC, for prior to and during treatment with Piqray, on the management of hyperglycemia, particularly focusing on testing fasting glucose (FG) and HbA1c, and optimizing blood glucose levels prior to treatment initiation; monitoring FG and HbA1c during treatment; and management of hyperglycemia if it occurs.

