#### [ON-LINE SURVEY - PROGRAMMER: RANDOMISE THE ORDER OF THE FIRST 4 RESPONSE OPTIONS]

7. According to the Piqray Prescriber's/HCP Guide for Hyperglycemia and SmPC for Piqray, please indicate if the following statement is True or False: For patients at higher risk for developing hyperglycemia, there is no need to consult with a healthcare professional or endocrinologist experienced in the treatment of hyperglycemia.

🗆 True

✓ False

□ I don't know/am not sure

8. According to the Piqray Prescriber's/HCP Guide for Hyperglycemia and SmPC for Piqray, to mitigate risk of hyperglycemia, which of the following should be performed before a patient starts treatment with Piqray?

|   |  | Check the box if
the action should
be performed |
|---|--|---|
| Α | Obtain a fasting glucose and
HbA1c  | 1   |
| В | Optimize the patient's level of
blood glucose, as applicable                      | 1   |
| с | Counsel the patient about the risk of hyperglycemia                                  | 1   |
| D | Increase the dose of their current
antihyperglycemic medication, if
applicable |   |
| E | Consult with a diabetologist for
all patients, even if they are not
diabetic   |   |
| F | I don't know/am not sure   |   |

[ON-LINE SURVEY - PROGRAMMER: RANDOMIZE THE ORDER OF THESE 5 QUESTIONS]  According to the Piqray Prescriber's/HCP Guide for Hyperglycemia and SmPC for Piqray, please indicate if the following statement is True or False: The monitoring schedule of fasting glucose levels for patients receiving Piqray is the same for patients with, and without, risk factors for hyperglycemia.

D True

✓ False

□ I don't know/am not sure

10. According to the Piqray Prescriber's/HCP Guide for Hyperglycemia and SmPC for Piqray, at what frequency should fasting glucose testing be performed for all patients treated with Piqray?

□ Weekly for the first 3 months of treatment, then monthly thereafter

✓ At weeks 1, 2, 4, 6, and 8 after treatment start, then monthly thereafter □ Daily for the first 2 weeks of treatment, then at Weeks 4, 6, and 8, then monthly thereafter

□ I don't know/am not sure

[ON-LINE SURVEY - PROGRAMMER: RANDOMIZE THE ORDER OF THE FIRST 3 RESPONSE OPTIONS]

11. According to the Piqray Prescriber's/HCP Guide for Hyperglycemia and SmPC for Piqray, at what frequency should HbA1c testing be performed for all patients treated with Piqray?

Monthly for the first 3 months of treatment, then quarterly thereafter

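### Key item 8A asks about fasting glucose and HbA1c in one tick box, so a tick cannot show whether an HCP knows both baseline tests or only one

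*Protocol*

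**What the plan says.** - **Definition and scoring.** Table 7-1 (Section 7.3.1) lists 8A as a key question on the two baseline tests together: "Knowledge that a fasting glucose and HbA1c should" be obtained before treatment. The operational definition is that row 8A is checked.
- **Questionnaire.** In Appendix 13.1, question 8, row A reads "Obtain a fasting glucose and" HbA1c, in a single cell with a single box. The other rows concern optimising blood glucose, counselling, raising a current medication dose, consulting a diabetologist, and not knowing. None names a single baseline test.
- **Composite.** Section 7.3.1 says the primary endpoint is "aggregated across the following survey questions: 4A, 5A-C, 6, 8A-C. 10, and 12-15", and is "calculated as the number of all correctly answered questions divided by the number of all answered questions". Success is a composite of at least 70%, and Section 7.7.2 judges this on the point estimate.
- **HbA1c elsewhere.** Question 11 is the only item on HbA1c alone. It asks how often to test during treatment, and it is not in the composite.
- **Importance.** Section 6 describes the Guide as "particularly focusing on testing fasting glucose (FG) and HbA1c", both before treatment starts and during it.

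**The concern.** The item joins two separate actions, and the answer is one tick. A respondent who would order both tests and a respondent who would order only a fasting glucose can give the same answer. The second has no narrower row to choose, and leaving 8A blank would deny a test they believe is needed. Table 7-1 nevertheless reads every tick as knowledge of both.

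Two results are affected. The item-level secondary result for 8A would be reported as knowledge of both tests when it may be knowledge of at least one. The primary composite takes in the same answer, and this is the only place where it touches HbA1c at all.

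The statistical analysis plan cannot repair this. Once the answer is collected as one tick, no analysis can separate the two tests, and Section 7.6 rules out going back to respondents to clarify knowledge answers.

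**Working it through.** **Inputs from the Protocol**
- Composite items listed in Section 7.3.1: 4A, 5A, 5B, 5C, 6, 8A, 8B, 8C, 10, 12, 13, 14, 15, which makes 13.
- Table 7-1 and the questionnaire also mark 5F, 5G and 5H as key. Counting them gives 16, so both counts are carried below.
- Threshold: 70% on the point estimate.
- Stated precision at 70% (Section 7.5): 17.4 points for 30 HCPs and 13.4 points for 50.

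**Assumed input.** Let q be the share of all HCPs who tick 8A while knowing only one of the two tests. The Protocol gives no figure. The range 5-20% is shown, with 100% as the ceiling.

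**Step 1. Reproduce the Protocol's precision.** Exact (Clopper-Pearson) 95% limits:
- 21 of 30: 50.6% to 85.3%. Half-width (85.3 − 50.6)/2 = 17.35, agreeing with 17.4 after rounding.
- 35 of 50: 55.4% to 82.1%. Half-width (82.1 − 55.4)/2 = 13.35, agreeing with 13.4.

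**Step 2. Weight of 8A.** If every HCP answers every item, 8A contributes 1/13 = 7.7% of the composite, or 1/16 = 6.25%.

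**Step 3. Effect of wrong credit.** Rise in the composite = q/13 or q/16. The other columns show what a reported 70% would become if 8A credit required knowledge of both tests.

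| q (assumed) | Rise, 13 items | 70% becomes | Rise, 16 items | 70% becomes |
|---|---|---|---|---|
| 5% | 0.4 | 69.6% | 0.3 | 69.7% |
| 10% | 0.8 | 69.2% | 0.6 | 69.4% |
| 20% | 1.5 | 68.5% | 1.25 | 68.75% |
| 100% (ceiling) | 7.7 | 62.3% | 6.25 | 63.75% |

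**Step 4. When the verdict could change.** A reported composite R falls below 70% only if q > 13 × (R − 70%). For R = 71% this needs q above 13%; for R = 72%, above 26%. With 16 items the figures are 16% and 32%. At q of 20% or less, only reported values from 70% to about 71.5% (13 items) are exposed.

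**Step 5. The item-level result.** There is no dilution here: the 8A percentage is overstated by q itself, so by 5-20 points over the same range.

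**Step 6. Is baseline HbA1c measured elsewhere?** Composite items 10, 12, 13, 14 and 15 concern fasting glucose. Item 8B concerns optimising blood glucose. Question 11 concerns HbA1c after treatment has started. None measures knowledge of the baseline HbA1c test.

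**The case against.** The strongest reply is that nothing here is contradictory. Section 6, Table 7-1 and the questionnaire all present the two tests as one baseline message, and no section promises a separate HbA1c measure within the composite. That is correct, and the point is therefore about an item that is badly fixed, not about inconsistent text.

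A reader might infer that every HCP who knows one test is credited with both. The documents do not support this. Credit follows only if the box is ticked, and an HCP who thinks HbA1c unnecessary may read the row as a pair and leave it blank. That HCP is scored as Table 7-1 intends, although the one test they do know then goes unrecorded. Over-credit is plausible because no narrower row exists, but its extent is unknown.

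A reader might also infer that question 12 has the same defect, since it too joins two recommendations ("adjustment is required, and it is recommended to" manage with oral treatment). It does not. It is a True/False statement with an explicit False option, so a respondent who rejects either half can say so and is scored incorrect. No change to question 12 is proposed.

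Finally, a separate HbA1c row would still name the answer, and some HCPs unaware of the recommendation may tick it. That limit stands, but every checklist item in this survey shares it. Splitting the row removes the ambiguity between the two tests; it does not remove recognition cueing.

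**Conclusion.** The point holds as a measurement weakness in one key item. As worded, 8A cannot support the claim that Table 7-1 attaches to it, and knowledge of baseline HbA1c, part of a named focus of the Guide, is isolated nowhere in the survey.

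The effect on the primary endpoint is modest: about 0.4-1.5 composite points (0.3-1.25 with 16 items) if 5-20% of HCPs are wrongly credited, and never more than 7.7 (6.25). This rests on the assumed share and on all items being answered. It is well inside the stated 13.4-17.4 point precision and can change the success verdict only when the composite lands close to 70%. A reader might conclude that the survey is built to pass its threshold; the documents do not show that, since neither the direction nor the size of the error is established. The item-level result for 8A is more exposed, because it carries the whole error. No sample-size or precision figure changes.

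**What to change.** Before launch:
- In question 8, replace row A by two rows, *Obtain a fasting glucose* and *Obtain an HbA1c*, within the same randomised list.
- In Table 7-1, score 8A as one composite item that is correct only if both rows are ticked, and count the pair once in the denominator. The number of composite items then stays as it is.
- Report each of the two rows separately as a secondary result.
- Update the randomisation instruction for question 8, which now refers to five rows, and the translations.

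The cost is one more row to program and translate, a few seconds per respondent, and a composite that may come out slightly lower. Appendix 13.1 refers to a pre-testing version of the questionnaire, so the change can be made there. After data collection it cannot be made at all.
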